- Participants were prohibited from having an autoimmune disease. Treatment of autoimmune diseases typically requires immunosuppressive therapies, the effects of which remain uncharacterized, vis-à-vis, atezolizumab immunotherapy. It is also imperfectly understood how checkpoint inhibition with atezolizumab may impact symptoms and progression of autoimmune diseases. For similar reasons, participants in prior studies were required to have disease that did not require treatment with systemic corticosteroids and/or other systemic immunosuppressive medications
- Participants were not allowed to have severely reduced kidney function (i.e., glomerular filtration rate  $\leq$  30 mL/min), a condition associated with poor health in general and a potentially increased risk of immune-mediated renal toxicity
- Participants were not allowed to be positive for HIV

Because cancer of the urinary tract is a heterogeneous disease (Kaufman et al. 2009), earlier atezolizumab studies were also restricted to relatively specific classes of patients, thereby limiting the number of additional factors that could complicate the final analyses. For example:

- Participants were only enrolled with advanced urothelial carcinoma. This restriction was easily tenable based on the fact that > 90% of bladder cancer cases have a urothelial histology (American Cancer Society 2016a), ensuring that the majority of clinical cases were being addressed in the trials
- Participants were required to have advanced on platinum-doublet therapy prior to entering the studies. This again made sense since platinum-doublet is standard first-line treatment of advanced UC (Bellmunt et al. 2014) and, thus, the majority of clinical cases should have been eligible for the study
- Finally, participants were prohibited from enrolling with CNS metastases, except in some highly defined situations if the metastases were asymptomatic. Although rare, CNS metastases in bladder cancer appear to be increasing in incidence and are associated with significant health burden and poor outcomes (Dhote et al. 1998; Protzel et al. 2002; Boyle et al. 2013; Chung et al. 2013). From both a safety perspective and a scientific perspective (e.g., the role of the blood-brain barrier in antibody drug delivery), inclusion of this class of patients in earlier atezolizumab trials was deemed premature

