## 6.6 SUBGROUP ANALYSES

Key safety and/or efficacy parameters will also be analyzed by the following subgroups:

- ECOG Performance status: 0–1 vs. 2
- Presence of CNS metastases at baseline: yes vs. no
- Renal impairment at study entry: yes vs. no
- Patient requiring dialysis: yes vs. no
- HIV status: negative vs. positive
- History of autoimmune disease: yes vs. no
- Progression on, or within 12 months of, prior platinum-based treatment: yes vs. no
- Concomitant steroid treatment ongoing at baseline: yes vs. no
- History of non-urothelial urinary tract carcinoma histology: yes vs. no
- Previous lines of cancer therapy (1 vs. 2 vs. 3)
- Age-adjusted Charlson comorbidity index (AACI):  $\leq 11$  vs.  $> 11$
- PD-L1 expression: low vs. high (cut-offs to be defined)
- Region (grouping countries into regions will be specified in the Statistical Analysis Plan)

All subgroup analyses will be based on the same methods as overall analyses of the primary and secondary variables. In addition, graphical displays such as forest plots will be used to descriptively visualize the homogeneity of key safety and efficacy parameters (proportions and 95% CI, or KM medians and corresponding 95% CI, as applicable will be displayed) across different levels of the pre-specified subgroup variables.

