 - PD-L1 expression by IHC class (IC0 to IC3)
 - PD-L1 expression: IC0/1 or IC2/3

Renal dialysis reported at baseline is defined as 'No' for all patients included with protocol version < 5 (regardless if any or no dialysis reported or no information given). For patients included with protocol version 5 or higher, if patient reports dialysis at Screening or Cycle 1 Day 1, then renal dialysis is set to 'Yes', otherwise if no dialysis is reported or if information is missing then renal dialysis is set to 'No'.

The time from diagnosis of primary disease to start of study treatment will be calculated in units of years as the difference between the date of start of study treatment and date of diagnosis of primary disease plus 1, divided by 365.25. For the calculation of the time from diagnosis of primary disease to start of study treatment, replacement rules will be applied in case the date of diagnosis of primary disease is incomplete. If day and month are missing, they will be imputed by June 30th to allow for time calculation, if only the day is missing, it will be imputed by 15. If after imputation, the date of diagnosis of primary disease is later than the start date of study treatment, then it will be set to the start date of study treatment.

The time from diagnosis of primary disease to diagnosis of metastatic disease will be calculated in units of years as the difference between the date of occurrence of metastatic disease and date of diagnosis of primary disease plus 1, divided by 365.25. For the calculation of the time from diagnosis of primary disease to diagnosis of metastatic disease, replacement rules will be applied for both dates in case dates are incomplete. If day and month are missing, they will be imputed by June 30th, if only the day is missing, it will be imputed by 15. If after imputation, the date of diagnosis of primary disease is later than the date of diagnosis of metastatic disease, then it will be set to the date of diagnosis of metastatic disease.

Creatinine clearance at baseline will be calculated using the Cockcroft-Gault formula:

$$\text{Creatinine clearance}[\text{mL / min}] = \frac{(140 - \text{age}[\text{years}]) \times \text{weight}[\text{kg}] \times (0.85 \text{ if female or } 1.0 \text{ if male})}{72 \times \text{serum creatinine}[\text{mg / dL}]}$$

A patient will be defined as having renal impairment in case creatinine clearance at baseline is < 30 mL/min.

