4.4.5 Subgroup Analyses

Secondary efficacy endpoints are also analyzed by the following subgroups:

- ECOG Performance status: 0–1 vs. 2
- Presence of CNS metastases at baseline: yes vs. no

- Renal impairment at study entry: yes vs. no
- Creatine clearance at study entry (mL/min): 15-<30 vs 30-<60 vs >=60
- Sex: female vs. male
- HIV status: negative vs. positive
- Patients aged ≥ 65 years: yes vs. no
- Patients aged ≥ 70 years: yes vs. no
- Patients aged ≥ 75 years: yes vs. no
- Patients aged ≥ 80 years: yes vs. no
- Patients aged 65-<75 vs 75-<80 vs ≥ 80
- History of autoimmune disease: yes vs. no
- Progression on, or within 12 months of, prior platinum-based treatment: yes vs. no
- Concomitant steroid treatment ongoing at baseline: yes vs. no
- History of non-urothelial or mixed urinary tract carcinoma histology: yes vs. no
- Tumor location: Ureter vs Renal Pelvis vs all UTUC (Ureter or Renal Pelvis) vs Bladder
- Prior Lines of Treatment for Metastatic Disease (0 vs 1 vs. 2 vs. 3)
- Age-adjusted Charlson comorbidity index (AACI): ≤ 11 vs. > 11
- PD-L1 expression: IC2/3 vs. IC0/1
- PD-L1 expression by IHC Class: IC0 to IC3
- IMvigor211-like patients: yes vs. no
- Region: Australia/Canada/Western Europe vs Eastern Europe vs Other regions

All subgroup analyses are based on the same methods for statistical analyses of the respective secondary efficacy endpoint. Graphical displays such as forest plots are used to visualize the homo-/heterogeneity of secondary efficacy endpoint results across different levels of the subgroups defined above (proportions and 95% CI, or KM medians and corresponding 95% CI as applicable).

The subgroup PD-L1 expression will be derived from the percentage of tumor area infiltrating immune cells as follows:

IC=0 (<1%), IC=1 ($\geq 1\%$ - <5%), IC=2 ($\geq 5\%$ - <10%), IC=3 ($\geq 10\%$).

The subgroup “IMvigor211-like patients” is defined as follows:

Patients with:

- ECOG Performance status: 0–1
- Presence of CNS metastases at baseline: no
- Renal impairment at study entry: no
- Patient with renal dialysis reported at baseline: no
- HIV status: negative
- History of autoimmune disease: no

- Progression on, or within 12 months of, prior platinum-based treatment: yes
- Concomitant steroid treatment ongoing at baseline: no
- History of non-urothelial or mixed urinary tract carcinoma histology: no
- Prior Lines of Treatment for Metastatic Disease: 0 or 1 or 2
- Patients aged ≥ 65 years: indifferent

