AEs with onset on first dosing date, not recorded as starting before study treatment administration will be considered as TEAEs. Similarly, AEs with onset date prior first dosing date but worsening/change recorded on or after first dosing date will be considered as TEAEs.

Only TEAEs will be included in summary tables. AEs which are not treatment-emergent will only be included in the AE listings.

Patient rates for AEs will be presented and accompanied by the respective two-sided 95% Pearson-Clopper CIs.

In any AE summary tables, number and percentage of patients reporting at least one AE will be provided. In AE summary tables by SOC and PT, the number of reported events will be presented additionally.

Every occurrence of an AE in any patient will be counted in the total number of events.

In tables presenting frequency of AEs by worst grade, only the event with the highest grade will be counted when there are multiple occurrences of a same AE in one patient.

A missing NCI CTCAE grade will be imputed as follows: for a fatal AE, as Grade 5; for a non-fatal AE, as Grade 4.

A summary table will be provided presenting:

- Number and percentage of patients with any TEAE
- Number and percentage of patients with any Serious TEAE
- Number and percentage of patients with any related TEAE
- Number and percentage of patients with any related Serious TEAE
- Number and percentage of patients with any TEAE leading to study drug discontinuation
- Number and percentage of patients with any grade 3 to 4 TEAE
- Number and percentage of patients with any grade 5 TEAE
- Number and percentage of patients with any AESI
- Number and percentage of patients with any grade 3 to 5 AESI
- Number and percentage of deaths, overall and by reason
- Number and percentage of deaths on study treatment (i.e. within 30 days post last study treatment administration), overall and by reason

Following safety data will be summarized:

- TEAEs by SOC, PT and by worst grade
- TEAEs of grade 3 to 5, by PT and by worst grade
- TEAEs of grade 5, by PT
- TEAEs leading to study drug discontinuation, by SOC and PT
- TEAEs leading to study discontinuation, by SOC and PT
- TEAEs related to study drug, by SOC, PT and worst grade
- Serious TEAEs by SOC, PT and worst grade
- Serious TEAEs related to study drug, by SOC and PT
- AEs of special interest by category, PT and worst grade (with additional column for AESI of grade ≥ 3)

Death cases will be summarized as follows:

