- Number of death events, overall and by primary cause of deaths, occurrence of an autopsy, number of death events within 30 days/ later than 30 days to 90 days and later than 90 days after first study treatment administration, number of death events within 30 days/ later than 30 days to 90 days and later than 90 days after last study treatment administration
- Number of death events by number of cycles started (1 cycle, 2 cycles, 3 cycles, 4 cycles, 5 cycles or more and broken down by number of days since last dose: ≤ 30 days, $>30 - \leq 90$ days or >90 days) and by primary cause of death and occurrence of an autopsy. A death event will be associated with the number of cycles the patient received, a cycle being counted when dose >0 . A summary table and the corresponding figure will be provided.

By-patient listings based on the safety population will be provided for the following types of AEs:

- TEAEs and AEs who do not meet the criteria of TEAEs
- AEs of special interest
- AEs leading to permanent treatment discontinuation
- SAEs
- Fatal AEs (i.e. grade 5 AEs)

In addition, a by-patient listing of death case will be provided based on the Safety Population. Deaths events will be categorized in days since first dose and days since last dose: ≤ 30 days, $>30 - \leq 90$ days or >90 days in this listing.

In the above listings, information relative to the following subgroups of interest will be included:

- ECOG Performance status: 0–1 vs. 2 (the category 2 includes patients who recorded status 2 at screening but 3 at baseline)

- Progression on, or within 12 months of, prior platinum-based treatment: yes vs. no
- Concomitant steroid treatment ongoing at baseline: yes vs. no
- History: non-urothelial or mixed urinary tract carcinoma histology vs urothelial
- AACI: ≤ 11 vs. > 11
- Renal impairment at study entry: yes vs. no
- Sex: female vs. male
- HIV status: negative vs. positive
- History of autoimmune disease: yes vs. no
- Presence of CNS metastases at baseline: yes vs. no
- Patients: < 65 years vs. ≥ 65 years
- Patients: < 70 years vs. ≥ 70 years
- Patients: < 75 years vs. ≥ 75 years
- Patients: < 80 years vs. ≥ 80 years
- Prior Lines of Treatment for Metastatic Disease: 0 vs 1 vs. 2 vs. 3
- PD-L1 expression: IC2/3 vs. IC0/1
- PD-L1 expression: IC0 to IC3
- IMvigor211-like patients: yes vs. no
- Regions: Australia/Canada/Western Europe vs Eastern Europe vs Other regions

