In addition, the AE summary table described previously in this section will be repeated for each of the above subgroups.

A by-patient listing of immune-related thyroid disorders on the safety population will also be provided.

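### No planned table gives the rate of nephritis, or of creatinine worsening, by renal impairment, although the protocol names renal toxicity as a possible added risk in that group

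*SAP*

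**What the plan says.** Protocol 1.4 explains that earlier studies excluded severely reduced kidney function, calling it "a condition associated with poor health in general and a potentially increased risk of immune-mediated renal toxicity". It then lists, among the broadened criteria, a clearance limit of 15 instead of 30 mL/min. Protocol 6.6 promises key safety and/or efficacy parameters by subgroup, renal impairment included, and adds: "All subgroup analyses will be based on the same methods as overall analyses of the primary and secondary variables".

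The SAP defines the subgroup in 4.3: "A patient will be defined as having renal impairment in case creatinine clearance at baseline is < 30 mL/min". SAP 4.6.2 makes nephritis an AESI category of its own and plans three kinds of AE output:

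- An overview table. Its AESI content is "Number and percentage of patients with any AESI" and the same count for Grade 3 to 5.
- Detailed tables, including "AEs of special interest by category, PT and worst grade".
- By-patient listings of AEs, AESIs and serious AEs that carry subgroup flags, among them "Renal impairment at study entry: yes vs. no".

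The section then states which output is produced by subgroup: "In addition, the AE summary table described previously in this section will be repeated for each of the above subgroups". The detailed tables are not mentioned there. SAP 4.6.3 plans shift tables of baseline against worst on-treatment grade for CTCAE-graded laboratory parameters, with no subgroup split.

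**The concern.** The trial's main purpose is to describe safety in a population that includes patients earlier studies screened out. For one such group the protocol names a particular harm. The SAP defines that group and gives the matching event its own category, but no planned table brings the two together.

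Followed as written, the tables show nephritis either over all treated patients, where an excess in a small group is diluted, or inside the any-AESI row for the renally impaired, where it is mixed with pneumonitis, thyroid disorders, infusion reactions and the rest. The report could then answer the renal question only by hand-counting from listings, with no stated rate or interval.

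**Working it through.** **1. Which planned outputs answer the question**

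| Output (SAP) | Shows nephritis separately? | Split by renal impairment? | Rate and interval? |
|---|---|---|---|
| AE overview (4.6.2) | No, AESIs pooled | Yes | Yes |
| AESI by category, term and grade (4.6.2) | Yes | No | Yes |
| By-patient AESI, serious AE and AE listings (4.6.2) | Yes | Flag only | No |
| Laboratory shift tables (4.6.3) | Creatinine, taken here as a graded parameter | No | No interval stated |

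SAP 4.4.5 does refer to adverse event and death tables in the plural by subgroup, but only for PD-L1 expression, further divided by similarity to the IMvigor211 population or by prior lines. Even on a broad reading this does not isolate renal impairment.

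**2. The plan's own precision figure**

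The method is the two-sided exact Clopper-Pearson interval: lower limit is the 0.025 quantile of Beta(x, n−x+1), upper limit the 0.975 quantile of Beta(x+1, n−x). For 5/1000 this gives 0.16% to 1.16%, half-width 0.50%, as in SAP 2.3. All nine rows of that table reproduce.

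**3. Dilution (assumed inputs)**

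The documents give neither the number of renally impaired patients nor a nephritis rate. Assume 50 impaired patients with 8% renal events (4) and 950 others with about 1% (10).

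- Planned table: (4 + 10)/1000 = 1.4%, 95% CI 0.8 to 2.3%.
- Split table: 4/50 = 8.0% (2.2 to 19.2%) against 10/950 = 1.1% (0.5 to 1.9%). The intervals separate.

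**4. Masking in the any-AESI row (assumed inputs)**

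The nearest documented background is the earlier study's immune-mediated AE rate, 20/310 = 6.45% (Protocol 1.3.4). It is an imperfect proxy for the AESI list. Add an independent 5% nephritis rate in the impaired:

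- Any AESI: 1 − (1 − 0.0645)(1 − 0.05) = 11.1%.
- With 100 impaired patients: 11/100 has 95% CI 5.6 to 18.8%, which still covers 6.45%.
- A nephritis row would show 5/100, 1.6 to 11.3%. Its lower limit is above 1.18%, the upper limit for the 0/310 immune-mediated renal events in that study.
- With 50 impaired patients the expected count is 2.5. At 2/50 the interval is 0.5 to 13.7%, which does not clear 1.18%. The gain therefore depends on subgroup size.

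**5. Precision of the added table**

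With no nephritis events the upper 95% limit is 16.8% for n = 20, 7.1% for n = 50 and 3.6% for n = 100. With 50 patients the chance of seeing at least one event is 39% if the true rate is 1% and 92% if it is 5%. The table is descriptive, far from the ±0.5% quoted for 1000 patients.

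**The case against.** The strongest reply is that nothing goes unreported. The AESI, serious AE and AE listings carry the renal flag, and SAP 4.3 plans the frequency of patients with and without renal impairment. In the example of step 3, a reader could count four flagged events and divide by 50. This stands. A reader might infer that renal toxicity in these patients disappears from the report, and the documents do not support that. What is missing is a tabulated rate with its interval, which 4.6.2 otherwise attaches to patient rates for AEs.

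Second, a reader might infer that the SAP breaches Protocol 6.6. That section covers key safety parameters without defining them, and its sentence on methods governs how parameters are analysed, not which tables are repeated. An overview with AESI rows is a defensible reading.

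Third, the shift table already arranges patients by baseline grade, so creatinine worsening is not shown as one pooled figure. Baseline grade is not the same as Cockcroft-Gault clearance below 30 mL/min, however, so the subgroup cannot be read from it.

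Fourth, the SAP's efficacy subgroups include "Creatine clearance at study entry (mL/min): 15-<30 vs 30-<60 vs >=60" and the safety subgroups do not, which may look like a further omission. Since entry requires at least 15 mL/min, the lowest class is, among eligible patients, the renal-impairment group already in the safety list. Adding the split would only divide the others.

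Fifth, the any-AESI row is not always blind. With a 6% background and the rates of step 3, it would be 1 − 0.94 × 0.92 = 13.5%, about 7/50 = 14% (5.8 to 26.7%), against 1 − 0.94 × 0.99 = 6.9%, about 66/950 (5.4 to 8.8%). That is a visible doubling, though the intervals overlap and the row would not say which event caused it.

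**Conclusion.** The point holds in limited form. No planned table gives the rate of nephritis, or of creatinine worsening, by renal impairment, although the protocol's rationale links that group to a potentially increased risk of renal toxicity. This is a gap between the protocol's stated concern and the planned tables, and closing it is a worthwhile, inexpensive improvement. It does not bias any planned estimate.

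The size cannot be fixed from the documents. The contrast of 1.4% pooled with 8.0% against 1.1% rests on an assumed 50 impaired patients and assumed rates. The masking example also borrows a background rate from another study and assumes independence.

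A reader might extend the criticism equally to every newly admitted group. Protocol 1.4 names an organ-specific toxicity only for reduced kidney function, so the same table for other groups, such as autoimmune history, is optional.

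**What to change.** 1. In SAP 4.6.2, after the sentence that repeats the overview by subgroup, add that the existing table of AESIs by category, preferred term and worst grade will also be produced by renal impairment (yes, no).
2. In SAP 4.6.3, add that the creatinine shift table will be produced by renal impairment (yes, no), with the proportion whose grade worsens.
3. State the subgroup n and the Clopper-Pearson 95% interval for each rate. Label the outputs descriptive, and as added if other outputs already exist.

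The AESI category table may be extended to other newly admitted groups at the sponsor's discretion. The three-level clearance split is not needed.

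The cost is SAP wording and re-running existing programs with a flag that is already derived. No new data are collected and no clinical rule changes. The downside is a few more tables, with wide intervals if the subgroup is small: with 50 patients, zero events still leaves an upper limit of about 7%.

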4.6.3 Laboratory Data

Assessments of laboratory parameters including hematology, chemistry, coagulation and thyroid panel will be performed as follows:

- For parameters with corresponding NCI-CTCAE grading, shift tables will be provided displaying baseline versus worst NCI-CTCAE grade on treatment (last date of treatment + 21 days)
- For parameters with no corresponding NCI-CTCAE grading, summary statistics will be provided for baseline values, actual values and the change from baseline values at post-baseline time points

Additionally, by-patient listings of all laboratory data, including site and patient identifier will be generated based on the safety population. A by-patient listing of ALT, AST,

alkaline phosphatase (AP) and total bilirubin assessments for potential Hy's law cases will also be provided.

